APPENDIX A: ECOG Performance Status Scale

Grade	Description
0	Normal activity. Fully active, able to carry on all pre-disease performance without restriction.
1	Symptoms, but ambulatory. Restricted in physically strenuous activity, but ambulatory and able to carry out work of a light or sedentary nature (e.g., light housework, office work).
2	In bed <50% of the time. Ambulatory and capable of all self-care, but unable to carry out any work activities. Up and about more than 50% of waking hours.
3	In bed >50% of the time. Capable of only limited self-care, confined to bed or chair more than 50% of waking hours.
4	100% bedridden. Completely disabled. Cannot carry on any self-care. Totally confined to bed or chair.
5	Dead.

APPENDIX B: Brief Pain Inventory

STUDY ID# _____ HOSPITAL # _____

DO NOT WRITE ABOVE THIS LINE

Brief Pain Inventory (Short Form)

Date: _____/_____/_____ Time: _____

Name: _____

Last First Middle Initial

1. Throughout our lives, most of us have had pain from time to time (such as minor headaches, sprains, and toothaches). Have you had pain other than these everyday kinds of pain today?

1. Yes 2. No

2. On the diagram, shade in the areas where you feel pain. Put an X on the area that hurts the most.

3. Please rate your pain by circling the one number that best describes your pain at its **worst** in the last 24 hours.

0	1	2	3	4	5	6	7	8	9	10
No Pain										Pain as bad as you can imagine

4. Please rate your pain by circling the one number that best describes your pain at its **least** in the last 24 hours.

0	1	2	3	4	5	6	7	8	9	10
No Pain										Pain as bad as you can imagine

5. Please rate your pain by circling the one number that best describes your pain on the **average**.

0	1	2	3	4	5	6	7	8	9	10
No Pain										Pain as bad as you can imagine

6. Please rate your pain by circling the one number that tells how much pain you have **right now**.

0	1	2	3	4	5	6	7	8	9	10
No Pain										Pain as bad as you can imagine

APPENDIX C: FACT-G7

Below is a list of statements that other people with your illness have said are important. **Please circle or mark one number per line to indicate your response as it applies to the past 7 days.**

		Not at all	A little bit	Some- what	Quite a bit	Very much
GP1	I have a lack of energy.....	0	1	2	3	4
GP4	I have pain	0	1	2	3	4
GP2	I have nausea	0	1	2	3	4
GE6	I worry that my condition will get worse	0	1	2	3	4
GF5	I am sleeping well.....	0	1	2	3	4
GF3	I am able to enjoy life.....	0	1	2	3	4
GF7	I am content with the quality of my life right now	0	1	2	3	4

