2.2 Secondary Objectives

1. To determine the rate of overall survival of patients with metastatic sarcoma stable on chemotherapy whose lesions have undergone ablation. Overall survival is defined as the time from diagnosis of metastatic disease to the time of death.
2. To determine the effects of ablation on quality of life (QOL) as measured with the FACT-G7 validated survey.
3. To determine the effects of ablation on pain as measured by the Brief Pain Inventory (BPI)-Short form, a validated scale for assessment of pain.

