5.5 Evaluation for Severity of Pain and Quality of Life

Patients will be evaluated for severity of pain using the BPI-Short Form (Appendix B) with the assistance of a study coordinator at the following time points:

- Prior to ablation
- 1 day post-ablation
- 1 month post-ablation – from first procedure if more than 1 is done
- Time of disease progression

The patients are asked to answer the questions with respect to the lesion(s) treated. They are not given a copy of the BPI-Short Form and no prior responses are available to review on subsequent visits to minimize bias. Analgesic use following the tumor ablation will be recorded as well.

Patients will be evaluated on quality of life based on the FACT-G7 survey (Appendix C) with the assistance of the study coordinator at the following time points:

- Prior to ablation
- 1 day post-ablation
- 1 month post-ablation – from first procedure if more than 1 done
- Time of disease progression

They are not given a copy of the FACT-G7 form and no prior responses are available to review on subsequent visits to minimize bias.

These surveys may be administered over the phone.

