7.0 STUDY CALENDAR

Baseline evaluations are to be conducted within 3 weeks prior to start of protocol therapy. Scans and x-rays must be done no more than 3 weeks prior to the start of ablation.

	Baseline	Ablation	1 day after ablation	1 month after ablation	Follow-up ^d	Progression
Physical exam, incl. medical history, weight, VS, PS	X					
CBC	X					
CMP	X					
PT/PTT and INR	X					
Pregnancy test ^a	X					
IR evaluation ^b	X					
CT or PET scan					X ^d	
FACT-G7	X		X	X		X
BPI short form	X		X	X		X
Adverse events		X ^c				
Survival follow-up						X ^e

a: Women of childbearing potential only

b: Patients must have 10 or fewer treatable lesions when enrolled in the study and will be seen in consultation by an experienced interventional oncologic radiologist with evaluation of available PET, CT, MR, and US images for eligibility and lesion accessibility

c: Tracked for 30 days following ablation

d: The patients will be imaged as per routine care at the following time points: 6 weeks post first-procedure, every 9 weeks for the first year, every 12 weeks for the second year, and every 6 months for 5 years or until death or radiographic progression, whichever comes first.

e. After progression, patients will be followed every 3 months for survival only.

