11.2 Data Analysis

Possible covariates in the analysis include sex, age, number of lesions and total diameter of all ablated lesions. Descriptive statistics (mean, median, range and standard deviation) will be provided for continuous variables and frequencies will be tabulated for categorical variables for the patients. Kaplan-Meier survival estimates will be obtained for 3-month PFS for patients with ablation therapy. For categorical covariates such as sex, number of lesions (<5 vs. ≥5) and total diameter of all ablated lesions (10cm vs. ≥10cm), if there are sufficient number of patients in each stratum, Kaplan-Meier survival curves will be plotted for each stratum and log-rank test will be performed to test if 3-month PFS is significantly different across strata. Overall survival will be analyzed with the same strategy as for 3-month PFS.

To determine whether or not there is an improvement in quality of life (QOL), since the variables related to QOL are in ordinal scale and will be measured at baseline, one day post ablation, one month post ablation and at time of disease progression, the GEE analysis implemented in SAS PROC GENMOD will be used to take into account the correlation of repeated measures from the same subject. Contrast statements will be used to compare mean QOL scores between any two times. The same analysis strategy will be performed to determine if BPI changes over time.

All analyses will be two-sided at a significance level of 0.05 and will be performed with statistical software SAS 9.3.

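### The 1-day FACT-G7 looks back 7 days, so its contrast with baseline mostly reflects pre-ablation days and cannot isolate an early effect of ablation on quality of life

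*Combined protocol and SAP*

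**What the plan says.** Section 2.2 makes quality of life a secondary objective: "To determine the effects of ablation on quality of life (QOL) as measured with the FACT-G7 validated survey". The form in Appendix C tells the patient to "indicate your response as it applies to the past 7 days".

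Section 5.5 gives the form before ablation, "1 day post-ablation", at one month, and at progression. Sections 7 and 8 repeat this schedule. The one-month form has a stated anchor, "1 month post-ablation – from first procedure if more than 1 done"; the one-day form has none. For baseline, Section 7 says "Baseline evaluations are to be conducted within 3 weeks prior to start of protocol therapy".

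Section 11.2 says the QOL variables "will be measured at baseline, one day post ablation, one month post ablation and at time of disease progression", fits a GEE model, and adds: "Contrast statements will be used to compare mean QOL scores between any two times". It names no contrast as the one of interest. Nothing in the documents shortens the recall period for the one-day form or asks patients to answer only for the time since the procedure.

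**The concern.** The analysis treats the one-day score as a post-ablation state, but the form asks about a week that lies mostly before ablation. A contrast of that score with baseline largely compares one stretch of pre-ablation time with another. If ablation changes quality of life sharply in the first day, in either direction, the contrast will understate the change. A non-significant result could then be reported as no early effect when the form had little chance of showing one.

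The BPI in Appendix B shows that the problem lies in pairing this form with this visit, not in having a one-day visit. Its worst-pain and least-pain items look back 24 hours and its item 6 asks about current pain, so those items suit a one-day assessment. The two instruments share a schedule although their recall periods differ.

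**Working it through.** **Inputs.** Recall period 7 days (Appendix C). Early visit 1 day after ablation (5.5, 7, 8). Four assessment times (11.2). Baseline up to 3 weeks before ablation (7). Planned enrollment 36 and two-sided 0.05 (11.1, 11.2).

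**The plan's own figure.** No figure is stated for quality of life. The only design figure is N = 36 for the primary endpoint, and it reproduces under the normal approximation: [(1.960·√(0.2·0.8) + 0.842·√(0.4·0.6)) / 0.2]² = 35.8, so 36. It is used below only as a sample size.

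**Share of the recall window after ablation.** Post-procedure share = min(days since procedure, 7) / 7.
- Day 1: 1/7 = 14% after, 6/7 = 86% before.
- Day 7 or later: 7/7. The one-month form is wholly post-ablation.

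**Overlap with baseline.** If the baseline form is completed b days before ablation, the two windows share max(0, 6 − b) days: 6 for b = 0, 5 for b = 1, 3 for b = 3, and none for b = 6 or more. Section 7 permits all of these.

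**Contrasts affected.** Four times give 4·3/2 = 6 pairs, of which 3 use day 1. Dilution toward no change from baseline describes only one of the three, day 1 versus baseline. In the other two (day 1 versus 1 month, day 1 versus progression) the fault is that the day-1 score is not a clean post-ablation state to compare with.

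**What dilution does to detection.** This is an illustration under stated assumptions: 36 patients with both forms, a paired normal approximation, effects in SDs of within-patient change (the documents give no QOL SD), and pre-ablation days that match baseline. Let w be the weight that the answer gives to post-ablation time.
- Detectable mean change at 80% power: (1.960 + 0.842)/√36 = 0.467 SD. The true change needed is 0.467/w.
- Power for a true change d: Φ(6dw − 1.960) + Φ(−6dw − 1.960).

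| w | True change needed for 80% power | Power, d = 0.5 SD | Power, d = 1.0 SD |
|---|---|---|---|
| 1 (no dilution) | 0.47 SD | 85% | >99% |
| 1/2 | 0.93 SD | 32% | 85% |
| 2/7 | 1.63 SD | 14% | 40% |
| 1/7 (equal weighting) | 3.27 SD | 7% | 14% |

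**The item about the present.** One of the seven items, GF7, asks about the present moment. If it reflected day 1 fully, the other six were weighted equally over 7 days, and all items changed alike, the share for the total would be (6·1/7 + 1)/7 = 13/49 = 27%, close to the 2/7 row.

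**The case against.** Several points on the other side are sound and limit the conclusion.

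- **The form cannot measure an early effect at all.** A reader might infer this, and also that 14% is a ceiling. Neither follows. The 1/7 share rests on equal weighting of recalled days; patients may give more weight to the latest day, and GF7 asks about the present. The effect is diluted, not removed.
- **Six of seven days always precede ablation.** Section 5.5 does not say which session the one-day form follows when there are several. If it follows a session 6 or more days after the first, the whole window falls after the first session. The 6-of-7 share holds for single-session patients, or when the form follows the first session. In the staged case the score mixes recovery from an earlier session with one day after a later one, so it is still not a clean early reading.
- **The direction of bias is known.** Only partly. If baseline is taken 6 or more days earlier, the windows do not overlap, and the pre-ablation days on the day-1 form may differ from baseline for other reasons.
- **The one-month form has the same fault.** A reader might infer this because it counts from the first procedure. In the extreme case of a last session on day 21, the form falls 30 − 21 = 9 days after it and looks back over roughly days 2 to 9, which is wholly post-ablation. Section 3.1 counts its two- to three-week limit from the radiology evaluation, so the spacing between sessions may well be shorter. Counting from the first procedure is an explicit choice that matches the 30-day toxicity period in Section 5.6. Moving the anchor would be a trade-off, not the correction of an error.
- **The stakes are modest.** Quality of life is a secondary objective with no power claim, Section 11.2 frames the question as improvement, and early harm is also captured by the 24-hour BPI items and by 30-day tracking of adverse events related to the procedure. All of this is true, and it bears on priority. It does not make the planned day-1 tests interpretable.

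**Conclusion.** The mismatch is real and nothing in the documents resolves it. For a single session, or a form that follows the first session, about 6 of 7 recalled days precede ablation. The day-1 versus baseline FACT-G7 contrast then carries roughly 1/7 of an acute change under equal weighting, and more if recent days dominate recall. It cannot isolate the early effect of ablation. The other two day-1 contrasts lack a clean post-ablation score. A null day-1 result should not be reported as evidence of no early change.

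The power figures are illustrative and rest on the assumptions listed with them. The qualitative conclusion needs only the 7-day recall and the one-day visit. The QOL objective is not lost, because the baseline to 1-month comparison is already among the planned pairs, and the primary endpoint is untouched. This is worth correcting before analysis but does not threaten the trial's main conclusion.

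**What to change.** 1. In Section 11.2, exclude the day-1 FACT-G7 from the inferential contrasts and name baseline to 1 month as the QOL contrast of interest.
2. Either remove the day-1 FACT-G7 from Sections 5.5, 7 and 8, or keep it as a descriptive measure and state that its recall period is mostly pre-ablation.
3. Keep the 1-day BPI. Section 8 lists a single QOL form and no separate BPI form, so any edit to that schedule should say explicitly that the BPI is still collected on day 1.
4. If the day-1 FACT-G7 is kept, state in Section 5.5 which session it follows when there is more than one.

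The cost is a wording amendment and, if the form is dropped, one fewer questionnaire. The real downside is that FACT-G7 will no longer give an inferential reading of early quality of life; the early patient-reported information will come from the BPI.
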